# Protocol for hyperglycemia

During the first visit, the finger prick random glucose level of potential participants is 300 mg/dl or higher two times in a row, the RA will notify PI immediately. The potential participants will be informed of their glucose levels and asked to contact their healthcare provider immediately. The PI will withdraw the study participant to prevent severe hyperglycemic events and/or DKA.

Adverse events (AEs) will be reported according to IRB policies. Any adverse event requiring reporting will be reported no later than 10 working days to the IRB using the IRB form "Report of Unanticipated Problem Involving Risk to Participants or Others" (IRB Form #1105). Reporting will depend on adverse event severity:

### Grading of Severity

0: No AE or within normal limits.

1: Mild AE.

2: Moderate AE.

3: Severe AE resulting in inpatient hospitalization, or a persistent or significant disability/incapacity.

4: Life-threatening or disabling AE.

5: Fatal AE.

### 8.0 Statistical Considerations

Based on Sit Less V1's (IRB #221566) effect size of 0.71 for reducing sitting time, we estimated a minimum sample size of 66. To assess the scalability of Sit Less V2, we aim to recruit 80 patients. Eligible participants will include T2D patients from VUMC who report sitting for over 10 hours daily, own a smartphone, and do not currently use an activity tracker. We will screen potential participants using VUMC's electronic health records (EHR) and send recruitment messages via the My Health at Vanderbilt app. According to our EHR search, we have 2,125 eligible patients, and with a 4% recruitment rate — as seen with enrolling 7 participants monthly from Sit Less V1 — reaching a target of 80 participants within 12 months is achievable.

### Analysis Strategies

Aim 1: Acceptability outcomes will be reported as percentages or averages. Aims 2 & 3: Descriptive analyses are planned to characterize the study sample on all measures including baseline demographics and covariates. For this pilot study, exploratory linear mixed modeling will be used to provide descriptive statistics relative to treatment effects, both within- and between-groups effects on the primary and secondary outcomes over time. We will also estimate effect sizes for those outcomes.

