Outcomes will be measured at baseline and post-intervention. Specifically, we aim to: Aim 1: Determine the acceptability of the SB reduction intervention in T2D patients by evaluating satisfaction and compliance with the intervention.

Aim 2: Evaluate the preliminary efficacy of the SB reduction intervention on changes in total SB time and numbers of prolonged SB bouts.

Aim 3 (Exploratory Aim): Explore preliminary effects of the SB reduction intervention on light physical activity (total standing and stepping times), cardiometabolic markers (24-hour glycemic control, BMI, waist circumference, blood pressure, and patient-centered outcomes (confidence in reducing SB, habit strength for SB, and quality of life).

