#### 6. Fitbit

We will provide Fitbit (Inspire 3) to each participant. The Fitbit is not intended to be used as a medical device. All participants will have the ability to monitor physical activity, sleep, and heart rate with the Fitbit. All data from the Fitbit will be continuously streamed to the secure Fitbit servers. The study team member will assist participants in downloading the app and creating an account and will instruct them on how to use the device, with the official Fitbit user manual. When we create Fitbit accounts for research subjects, we do not use their real name or email address and default their account settings to the most privacy-protective option available.

Fitbit accounts require a unique email address for each user. To ensure participants' anonymity and privacy when creating Fitbit accounts, we will (1) set up anonymous Gmail accounts and (2) set up de-identified Fitbit accounts for the purpose of the study. This individualized email address will then be linked to a Fitbit account in which personal identifiers should not be used. Importantly, research staff and participants will be advised that the email and Fitbit accounts should be used strictly for the study's purpose.

Moreover, account information will be stored in protected PI's computer within encrypted documents. Once the intervention is concluded, Fitbit data will not be collected. Also, Fitbit and Fitbit app will be reset for the participant to keep using the Fitbit after study completion.

#### 5.2 Baseline visit 2

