### 5.2.2 Randomization

Once the data is downloaded and reviewed by the PI, the Study Team Member will use the REDCap randomization function and will inform participants of their group assignment (1:1 ratio).

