# 5.3.6 Control Group

The control group will receive the American Heart Association's Healthy Living booklet. Control group participants will receive all study assessment but will not be instructed to monitor sitting time. The Fitbit move alert setting will be disabled for the control group.

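### Section 8.0 lists within-arm change as a treatment effect beside the between-arm difference, and does not commit the mixed model to adjusting for the baseline value

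*Combined protocol and SAP*

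**What the plan says.** The efficacy analysis is described only in Section 8.0, under Analysis Strategies. For Aims 2 and 3, exploratory linear mixed modelling will "provide descriptive statistics relative to treatment effects, both within- and between-groups effects on the primary and secondary outcomes over time". The next sentence is "We will also estimate effect sizes for those outcomes", with no contrast and no standardizing SD. Baseline values and covariates appear only in a sentence about describing the sample: "Descriptive analyses are planned to characterize the study sample on all measures including baseline demographics and covariates". The fixed effects of the model are not given.

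Section 2.0 sets two outcome times: "Outcomes will be measured at baseline and post-intervention". Aim 2 is to "Evaluate the preliminary efficacy of the SB reduction intervention on changes in total SB time and numbers of prolonged SB bouts", which names no between-arm contrast. Section 5.2.2 gives 1:1 randomization.

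Both arms receive a Fitbit. Section 5.1, item 6 says "All participants will have the ability to monitor physical activity, sleep, and heart rate with the Fitbit", and Section 5.3.6 removes one function for controls: "The Fitbit move alert setting will be disabled for the control group".

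**The concern.** Change from baseline within an arm mixes the intervention with everything else that happens over eight weeks. The documents name several exposures that both arms share. All participants can monitor themselves with the Fitbit. The procedures common to both arms have the baseline activPAL report reviewed with participants at Baseline visit 2 (Section 5.1, item 3). Controls also receive a healthy-living booklet (Section 5.3.6). Only the between-arm contrast removes what the arms share, and it is the contrast that randomization protects. The plan reports that contrast, but does not say that it is the one that answers Aim 2 or supplies the effect size.

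The effect size matters because this program carries effect sizes forward: Section 8.0 sets the present sample size from the value of 0.71 seen in the previous version of the program.

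A second, smaller matter is precision. The plan's wording fits a baseline-adjusted model, but it equally fits the usual group, time and group-by-time model. With one value per person at two visits, the group-by-time contrast is the difference in mean change, which uses the baseline less efficiently than adjustment does.

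**Working it through.** **1. The plan's own figure.** Section 8.0 gives an effect size of 0.71 and a minimum of 66 participants. It states neither alpha nor power. Assume two-sided 5% and 80%. A two-sample t-test at d = 0.71 has power 0.798 at 32 per arm and 0.811 at 33 per arm, so 33 × 2 = 66, as stated. At the recruitment target of 80 (40 per arm) power is 0.88. A one-arm paired test at 0.71 would need only 18 people. The sample size therefore fits a between-arm comparison. The documents do not say which contrast or SD the 0.71 itself came from.

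**2. Precision of the between-arm estimate.** Inputs: 40 per arm (80 at 1:1), one summary value per person at each of two visits, equal variances (SD = 1), complete data. The baseline-post correlation r is not in the documents, so a range is assumed.

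- Unconstrained group-by-time model: per-person variance 2(1 − r).
- Baseline-adjusted model: per-person variance 1 − r².
- Variance ratio: 2(1 − r)/(1 − r²) = 2/(1 + r), so adjustment saves a fraction (1 − r)/2.
- 95% CI half-width: t(0.975) × √(variance × 2/n).

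Worked case, r = 0.5, n = 40:

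- Unconstrained: 1.991 × √(1.00 × 2/40) = 0.445.
- Adjusted: 1.991 × √(0.75 × 2/40) = 0.386.

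| r | Variance ratio | Variance saved | Half-width, unconstrained | Half-width, adjusted |
|---|---|---|---|---|
| 0.3 | 1.54 | 35% | 0.53 | 0.42 |
| 0.5 | 1.33 | 25% | 0.45 | 0.39 |
| 0.7 | 1.18 | 15% | 0.34 | 0.32 |
| 0.9 | 1.05 | 5% | 0.20 | 0.19 |

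At the minimum of 33 per arm the pairs are 0.58 and 0.47, 0.49 and 0.43, 0.38 and 0.35, 0.22 and 0.21. Chance baseline imbalance adds less than 0.004 to the adjusted values.

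**3. Why the SD must be stated.** The SD of change is √(2(1 − r)) times the raw SD. A between-arm difference of 0.71 raw SD, divided by the SD of change, becomes 0.71/1.183 = 0.60 at r = 0.3, 0.71/1.000 = 0.71 at 0.5, 0.71/0.775 = 0.92 at 0.7 and 0.71/0.447 = 1.59 at 0.9. The same result could be published as any of these.

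**The case against.** The plan calls itself a pilot, and its modelling exploratory and descriptive. It states no test, alpha or success rule. It names between-group effects explicitly and would report both contrasts, so a reader could see the control-arm change. The sample size suggests that the team already had a between-arm comparison in mind. All of this stands, and it makes the matter one of interpretation and efficiency, not of a wrong analysis.

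A reader might infer more: that the plan omits the between-arm comparison, that it will judge efficacy by within-arm change, that its between-arm estimate would be biased, or that 66 is wrong. The documents support none of these. The between-arm effect is planned, no rule rests on within-arm change, the unconstrained estimate is unbiased under randomization, and 66 reproduces under ordinary assumptions. Nor do the documents give the size of any change shared by both arms, so how far a within-arm effect would mislead cannot be calculated from them.

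The precision argument also has conditions. It depends on an unstated r, and on one summary value per person at two visits. The activPAL records seven days per period, and Section 5.3.5 adds a mid-program week for the intervention. If daily values or that week enter the model, the figures above no longer apply as they stand.

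What remains is that a pilot label does not turn within-arm change into a treatment effect. Under an aim of preliminary efficacy, the effect estimate and its interval are the main efficacy output, so their definition should be fixed beforehand.

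**Conclusion.** The point holds as a worthwhile improvement, not as an error that invalidates the plan. Section 8.0 should not list within-arm change as a treatment effect in a 1:1 randomized trial whose arms share a Fitbit, and it should commit to a baseline-adjusted between-arm contrast.

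The size of the precision gain rests on assumed correlations, equal variances, complete data and one value per person at two visits. At 40 per arm it narrows the half-width by about 0.10 SD at r = 0.3, 0.06 at 0.5 and 0.03 at 0.7, and by a negligible amount at 0.9. Adjustment does not cost meaningful precision at any of these values. The missing SD definition alone would be a gap in detail; the same change closes it.

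**What to change.** Add to Section 8.0, under Analysis Strategies:

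> For Aim 2 and Aim 3 outcomes measured at baseline and post-intervention, the treatment effect is the between-arm difference at post-intervention adjusted for the baseline value (ANCOVA, or a linear mixed model with a common baseline mean), with a 95% CI. The effect size is this difference divided by the pooled baseline SD. Within-arm changes are reported as description only.

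For count outcomes (prolonged sedentary bouts, glycaemic events) the same baseline-adjusted between-arm contrast applies, on a scale suited to counts where needed. Aim 1 outcomes such as satisfaction and usability have no baseline value and are unaffected.

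The planned mixed model can stay. With one baseline and one post value per person, ANCOVA and the common-baseline model give the same contrast when only post values are missing, so either will do. The cost is a few sentences: no new data, no new visits, and ANCOVA is a standard procedure in the SPSS software that Section 9.0 already names.

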### 9.0 Privacy/Confidentiality Issues

Date: May 15th, 2024

All Personal Health Information (PHI) and Personal Identifying Information (PII) will be kept confidential, unless release is required by law. Release of PHI/PII information will only be allowed if it is legally required by law. The PI and staff have been trained in confidentiality and HIPAA requirements and will conduct the study using Good Clinical Practice guidelines.

Upon enrollment, participants will be assigned a unique study ID number and anonymous email account that will be used to label all research data including Fitbit data, CGM data, questionnaires, and activPAL data. The study ID and the anonymous email will serve as the only identifier used on all study-related documents. Informed consent will occur at the time of recruitment once eligibility verification is completed. The participant identifiers will be stored in the Master List, which will include full name and contact information (e.g., phone number, email address) and will be used for administrative purposes only. The Master List will be maintained by study staff and stored in a file separate from the coded study dataset on a password-protected computer. Only individuals directly involved with the study (e.g., PI or her staff) will have access to this file.

This individualized email address will then be linked to a Fitbit account in which personal identifiers should not be used. Importantly, research staff and participants will be advised that the email and Fitbit accounts should be used strictly for the study's purpose. Moreover, account information will be stored in protected PI's computer within encrypted documents.

All the Fitbit data will be extracted from the Fitbit account to Redcap using the Fitbit web API developed by VU School of Nursing IT team. Fitbit data will be stored on a secure computer at University School of Nursing server and password-protected, only accessible by the PI and/or the IT team. The Fitbit data will be uploaded into REDCap.

To send weekly text messages from REDCap, we will utilize the third-party service Twilio.com which means that all voice calls and SMS messages will be routed through Twilio's servers. However, REDCap goes to great lengths to ensure that voice call records and SMS transcriptions do not stay in Twilio's logs but are removed shortly after being completed. This is done for security and privacy concerns (e.g., HIPAA), in which our survey participants' phone numbers and their survey responses do not get permanently logged on Twilio's servers but instead remain securely and separately in REDCap. Twilio uses two-factor authentication to access the application administratively. The integrated module can only be turned on by a REDCap Administrator. Twilio configuration is managed by a REDCap administrator. The integration requires 'inspectors' be turned off at the Twilio level to ensure no logging data is retained.

However, this method is limited to two-way interaction, which means that Twilio and REDCap system do not allow research participants to text back to the study team. To facilitate two-way communications, we will have a wireless cell phone and answer any questions if the participants have any.

All hard copy documents (e.g., sleep diary or wear log) will be stored in a locked filing cabinet and office. All electronic records, including the Master List and voice recordings, will be stored on a secure computer at Vanderbilt University School of Nursing and password-protected, only accessible by the PI and/or her staff. No identifiable information will be stored on any mobile devices (laptops, USB keys, CDs, DVDs, etc.). Research files will be kept for 7 years after the study is completed. Data entry will be completed in REDCap by the PI and/or her staff and will be imported to SPSS file format for analysis. Only de-identified data will be used for analysis.

### 10.0 Follow-up and Record Retention

Raw hard copy research data will be kept in locked file cabinets in a locked office. All electronic records, including the Master List and voice recordings, will be stored on a secure internal Vanderbilt University School of Nursing server and password-protected, only accessible by the PI and/or her staff. After a period of seven years from the end date of the study, all identifying information, including signed consent forms and the Master List, will be destroyed. Anonymous raw data and electronic data will be maintained indefinitely.

